1.0 HYPOTHESIS AND OBJECTIVES

Hypothesis

Ruxolitinib (also known as INCB018424), a JAK1/2 inhibitor, and lenalidomide (immunomodulatory inhibitory drug; IMiD) are effective and tolerable treatments for patients with myelofibrosis (MF). Combination of these agents in patients with MF can improve the overall clinical response to therapy without causing excessive toxicity.

Objectives

Primary:

- to determine the efficacy of the combination of INCB018424 with lenalidomide in patients with MF, in achieving objective improvements in disease status

Secondary:

- to determine the safety of the combination in patients with MF

Exploratory:

- to explore time to response and duration of response
- to explore the effect of the combination on anemia and transfusion dependence in patients with MF
- to explore changes in JAK2V617F allele burden

2.0 BACKGROUND AND RATIONALE

2.1 Myelofibrosis with Myeloid Metaplasia

Myelofibrosis with myeloid metaplasia (MF) is a rare clonal proliferative disorder of a pluripotent stem cell. This clone subsequently induces fibrogenic cytokines and/or growth factors in the marrow, which stimulate the deposition of extracellular matrix proteins by polyclonal fibroblasts. Megakaryocytic hyperplasia-dysplasia is frequently observed. Invasion of the blood stream and colonization of extramedullary sites ensues, resulting in organomegaly and splenomegaly. Extensive marrow fibrosis and osteosclerosis may be observed in advanced MF, resulting in “dry taps”.

The entity of MF can be either idiopathic (primary or agnogenic myeloid metaplasia), or representative of end-stage myeloproliferative diseases such as polycythemia vera (PV) or essential thrombocythemia (ET). MF occurs in about 25% of patients with PV and in 2% to 3% of patients with ET. In the early cellular phase of MF with minimal marrow fibrosis, the differential diagnosis includes Philadelphia-positive CML, PV, and ET that must be distinguished, based on cytogenetics and clinicopathologic features. Other entities that can induce myelophthisis include myelodysplastic syndrome (MDS), metastatic malignancies, lymphoma, Hodgkin’s disease, and plasma cell dyscrasias. MF must be differentiated from acute megakaryocytic leukemia (AML, M7 of the French-American-British classification) and MDS with fibrosis. In acute megakaryocytic leukemia patients usually present with severe constitutional symptoms and pancytopenia but without organomegaly or peripheral blood myelophthisis.

The clinical picture of MF involves constitutional symptoms (e.g., cachexia, night sweats, fatigue, fever), splenomegaly, anisopoikilocytosis with teardrop erythrocytes, progressive anemia, immature myeloid and erythroid precursors in the peripheral blood, elevated lactate dehydrogenase (LDH) levels, and fibrosis of the marrow (as evaluated by reticulin and trichome [collagen] stains). The leukoerythroblastic picture is postulated to be related to both the intramedullary sinusoidal marrow and splenic hematopoiesis.

The disease generally occurs in adults, with the median age ranging from 54 to 62 years; 70% of the patients are over the age of 50 years. In 40% of the patients, constitutional symptoms are present, including fever, weight loss, nocturnal sweating, pruritus, and bone pain. Splenomegaly is present in 85% of the patients at diagnosis, and is massive in 10%. Hematologic disease features include anemia in 50% to 70% at diagnosis and 25% will have severe anemia with hemoglobin level < 8.0 gm/dL. Approximately half of the patients present with an elevated white cell count (WBC), 28% with thrombocytosis (platelet count > 500 x 10⁹/L, and 37% with thrombocytopenia (platelet count < 150 x 10⁹/L). Circulating blast cells are present in one-third of the patients.

Complications of MF are varied. Thrombotic obliteration of intrahepatic veins and splenomegaly may lead to portal hypertension; severe cases may be associated with ascites and/or variceal bleeding. Left upper quadrant pain may herald splenic infarction; episodes are usually self-limited and may persist for several days. Supportive care measures such as analgesics and hydration are usually sufficient; refractory cases may require splenectomy or irradiation. Extramedullary hematopoiesis (EMH) may occur in locations other than the liver or spleen; involvement of such sites may be managed by low-dose irradiation. Liver involvement is associated with increased levels of plasma alkaline phosphatase. Clinical manifestations of EMH include cardiac tamponade, papular skin nodules, pleural effusions, and spinal cord compression.

Autoimmune phenomena have been observed, including Coomb's positive autoimmune hemolytic anemia, nephrotic syndrome, antinuclear antibodies, rheumatoid factor, and lupus-type anticoagulant. Postulated etiologies include clonality of the lymphoid population or activation by abnormal monocyte-macrophage interaction with the immune system.

Adverse prognostic factors for survival include older age and anemia (hemoglobin < 10 gm/dL). The etiology for the latter finding is usually multifactorial and related both to marrow failure and hypersplenism. Poor prognosis has also been correlated with leukocytosis, leukopenia, circulating blasts, increased numbers of granulocyte precursors, thrombocytopenia, abnormal karyotype, and hypercatabolic symptoms. The course of the disease is highly variable. Median survival from time of diagnosis ranges from 5 to 6 years. Progressive marrow failure, transformation into acute myeloid leukemia, and portal hypertension lead to demise.

No standard therapy exists for MF. Hydroxyurea is the most commonly used agent in the proliferative phases of the disease. Interferon-alpha had yielded hematologic

responses and reductions in splenomegaly (definitions varying among studies) especially those with proliferative phase, however, this agent tends to be poorly tolerated. Agents used for the management of anemia include androgens and/or erythropoietin. Splenectomy and/or splenic irradiation have been used to manage symptomatic splenomegaly. Splenectomy has been associated with risk of leukemia transformation in some series, and splenic irradiation can result in severe myelosuppression. No medical therapy has been proven to prolong overall survival for these patients. Patients with an intact quality of life and no threatening hematologic abnormalities, such as erythrocytosis or thrombocytosis, have usually been considered to not require any therapy.

In vitro data suggests that cytokines elaborated by megakaryocytes stimulate human bone marrow fibroblasts to divide and secrete collagens. In patients with MF, increased levels of transforming growth factor-beta (TGF-beta) have been observed in circulating peripheral blood mononuclear cells (PBMC) of megakaryocytic lineage.

Increased levels of basic fibroblast growth factor (bFGF) have also been reported in patients with MF. Both TGF-beta and bFGF are members of multifunctional polypeptide families that regulate cell growth and differentiation. In addition to their potent fibrogenic activity, TGF-beta and bFGF regulate hematopoiesis by selective actions on primitive stem cells. Expression of TGF-beta in early CD34+ hematopoietic stem cells negatively regulated the cycle status; this effect could be abrogated by bFGF. In addition, bFGF has been shown to augment the activity of stem cell factor (SCF), interleukin-3 (IL-3), granulocyte-macrophage colony stimulating factor (GM-CSF), or erythropoietin on committed progenitor cells. Other cytokines/proteins that are dysregulated in MF include; tumor necrosis factor-alpha (TNF-alpha) and angiogenic agents like vascular endothelial growth factor (VEGF).

2.2 INCB018424

Rationale

JAKs play an important role in signal transduction following cytokine and growth factor binding to their receptors. In addition, JAKs activate a number of downstream pathways implicated in the proliferation and survival of malignant cells including the STATs (signal transducers and activators of transcription), a family of important latent transcription factors. Aberrant activation of JAKs has been associated with increased malignant cell proliferation and survival in patients with Philadelphia chromosome negative MPD. The finding that peripheral blood from myeloproliferative disease (MPD) patients is capable of forming erythroid and megakaryocyte colonies in the absence of exogenous factors (which signal through JAKs) suggests that cells from these patients are intrinsically different than normal cells. Indeed, work from a number of laboratories led to the identification of multiple somatic mutations in genes associated with cytokine and growth factor signaling. These include a mutation in the pseudo-kinase domain of JAK2V617F (amino acid 617, valine to phenylalanine) that results in constitutive activation of JAK2 and downstream STATs. This mutation was found in > 90% of all PV patients and in approximately 50% of all ET and Myelofibrosis with Myeloid Metaplasia

(MMM) patients. More recently, other mutations have been identified in MPD patients lacking the JAK2V617F mutation. For instance, additional activating mutations in JAK2, as well as a mutation in the thrombopoietin receptor (MPL), result in constitutive ligand-independent JAK activation. Importantly, ectopic expression of each of these mutant genes has been demonstrated to be sufficient to cause MPD-like syndromes in mice. Moreover, even in MPD patients lacking a confirmed JAK2 mutation, the detection of STAT activation suggests dysregulated JAK activity. In fact, regardless of the mutational status of JAK2, the malignant cells expectedly retain their responsiveness to JAK activating cytokines and/or growth factors; hence, they may benefit from JAK inhibition. These findings, in addition to the limited life span of these patients and lack of beneficial therapies for the treatment of PMF and post-PV/ET MF, clearly support the evaluation of JAK inhibitor in these diseases. INCB018424 phosphate is an inhibitor of the Janus kinase family of protein tyrosine kinases (JAKs) that is currently under development for treatment of myeloproliferative disorders (MPD).

Clinical Experience

We conducted a phase 1–2 trial of INCB018424 in patients with *JAK2* V617F–positive or *JAK2* V617F–negative primary myelofibrosis, post–essential thrombocythemia myelofibrosis, or post–polycythemia vera myelofibrosis. A total of 153 patients received INCB018424 for a median duration of more than 14.7 months. The initial dose-escalation phase established 25 mg twice daily or 100 mg once daily as maximum tolerated doses, on the basis of reversible thrombocytopenia. A dose-dependent suppression of phosphorylated signal transducer and activator of transcription 3 (STAT3), a marker of JAK signaling, was demonstrated in patients with wild-type *JAK2* and in patients with the *JAK2* V617F mutation. We studied additional doses and established that a 15-mg twice-daily starting dose, followed by individualized dose titration, was the most effective and safest dosing regimen. At this dose, 17 of 33 patients (52%) had a rapid objective response ($\geq 50\%$ reduction of splenomegaly) lasting for 12 months or more, and this therapy was associated with grade 3 or grade 4 adverse events (mainly myelosuppression) in less than 10% of patients. Patients with debilitating symptoms, including weight loss, fatigue, night sweats, and pruritus, had rapid improvement. Clinical benefits were associated with a marked diminution of levels of circulating inflammatory cytokines that are commonly elevated in myelofibrosis.

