2.3 Lenalidomide

Lenalidomide is the lead compound in a proprietary class of Celgene compounds known as IMiDs® with immunomodulatory and anti-angiogenic properties that could confer antitumor and antimetastatic effects. It is a derivative of thalidomide, combining higher efficacy and lower toxicity than its parent compound. Lenalidomide has been demonstrated to possess anti-angiogenic activity through inhibition of bFGF, VEGF and TNF-alpha induced endothelial cell migration, due at least in part to inhibition of Akt phosphorylation response to bFGF. In addition, lenalidomide has a variety of immunomodulatory effects. Lenalidomide stimulates T cell proliferation, and the production of IL-2, IL-10 and IFN-gamma, inhibits IL-1 beta and IL-6 and modulates IL-12 production.

Clinical experience in myelofibrosis with lenalidomide

Two similarly designed but separate phase 2 studies involving single-agent lenalidomide in a total of 68 patients with symptomatic myelofibrosis were reported in one paper. Protocol treatment consisted of oral lenalidomide at 10 mg/d (5 mg/d if baseline platelet count < 100 x 10⁹/L) for 3 to 4 months with a plan to continue treatment for either 3 or 24 additional months, in case of response. Overall response rates were 22% for anemia, 33% for splenomegaly, and 50% for thrombocytopenia. Response in anemia was deemed impressive in 8 patients whose hemoglobin level normalized from a baseline of either transfusion dependency or hemoglobin level lower than 100 g/L. Additional treatment effects in these patients included resolution of leukoerythroblastosis (4 patients), a decrease in medullary fibrosis and angiogenesis (2 patients), and del(5)(q13q33) cytogenetic remission accompanied by a reduction in JAK2(V617F) mutation burden (1 patient). Grade 3 or 4 adverse events included neutropenia (31%) and thrombocytopenia (19%). Authors concluded that lenalidomide engenders an intriguing treatment activity in a subset of patients with MF that includes an unprecedented effect on peripheral blood and bone marrow abnormalities.

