To investigate the safety and efficacy of the combination of lenalidomide and prednisone in patients with MF, 40 patients were treated. Therapy consisted of lenalidomide 10 mg/d (5 mg/d if baseline platelet count < 100 x 10⁹/L) on days 1 through 21 of a 28-day cycle for six cycles, in combination with prednisone 30 mg/d orally during cycle 1, 15 mg/d during cycle 2, and 15 mg/d every other day during cycle 3. Lenalidomide therapy was continued indefinitely in patients exhibiting clinical benefit. The median follow-up was 22 months (range, 6 to 27). Responses were recorded in 12 patients (30%) and are ongoing in 10 (25%). The median time to response was 12 weeks (range, 2 to 32). According to the International Working Group for Myelofibrosis Research and Treatment consensus criteria, three patients (7.5%) had partial response and nine patients (22.5%) had clinical improvement durable for a median of 18 months (range, 3.5 to 24+). Overall response rates were 30% for anemia and 42% for splenomegaly. Moreover, 10 of 11 assessable responders who started therapy with reticulin fibrosis grade 4 experienced reductions to at least a score of 2. All eight JAK2^{V617F}-positive responders experienced a reduction of the baseline mutant allele burden, which was greater than 50% in four, including one of whom the mutation became undetectable. Grade 3 to 4 hematologic adverse events included neutropenia (58%), anemia (42%), and thrombocytopenia (13%). The combination of lenalidomide and prednisone induced durable clinical, molecular, and pathologic responses in MF.

Most frequently reported adverse events reported during clinical studies with lenalidomide in oncologic and non-oncologic indications, regardless of presumed relationship to study medication include: anemia, neutropenia, thrombocytopenia and pancytopenia, abdominal pain, nausea, vomiting and diarrhea, dehydration, rash, itching, infections, sepsis, pneumonia, UTI, Upper respiratory infection, cellulitis, atrial fibrillation, congestive heart failure, myocardial infarction, chest pain, weakness, hypotension, hypercalcemia, hyperglycemia, back pain, bone pain, generalized pain, dizziness, mental status changes, syncope, renal failure, dyspnea, pleural effusion,

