5.0 TREATMENT PLAN

Four weeks on therapy is considered one cycle of therapy. INCB018424 and lenalidamide will be given orally in an outpatient setting. INCB018424 will be given continuously daily in 28-day cycles, and lenalidamide will be given on days 1-21 of 28 day cycles. Dosage for cycles can be reduced, increased or delayed based assessment of efficacy and on adverse events, if any occur, as described below. Delays of a maximum of 8 weeks are allowed from scheduled next cycle.

Subjects will be asked to maintain a diary to record drug administration. Subjects will be asked to bring any unused study drug to the research center at their next visit. Research personnel will count and record the number of used and unused study drug capsules/tablets (both ruxolitinib and lenalidomide) at each visit and reconcile with the subject diary. The study coordinator will question the patient regarding adherence to the dosing regimen, record the number of capsules/tablets and strengths returned in the carton, the date returned and determine treatment compliance before dispensing new medication to the study patient. Compliance below 80% will require counseling of the patient by study site personnel.

The planned dose and schedule of investigation of INCB018424 is 15 mg orally twice daily (BID), continuously in 28-day cycles. Lenalidomide will be taken orally 5 mg/day in the morning each day on days 1-21, followed by 7 days of no therapy of each 28-day cycle; medication will be mailed to participants, per the RevAssist® Program.

Twenty eight days is considered one cycle of therapy. Attempts will be made to provide an adequate treatment period of at least 6 months unless significant toxicity observed, to account for delayed time to response observed with biologic agents. Responders will continue therapy for 6 years unless progression of disease or toxicity warranting discontinuation of therapy is observed.

Prednisone will be added for patients who have not responded after 3 cycles of therapy. It will be dosed orally at the dose of 30 mg/day during cycle 4, 15 mg/day during cycle 5, and 15 mg every other day during cycle 6, and then it will be discontinued.

All patients will be registered in the Clinical Oncology Research system(CORE) at MD Anderson Cancer Center after the informed consent is signed.

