5.1 Dose Modification

Dose Level mg BID	INCB018424 (Days 1-21 Q 4 weeks)	Lenalidomide QD
Dose Level +3	25	15
Dose Level +2	20	10
Dose Level +1	20	5
Level 0	15	5
Dose Level -1	10	5
Dose Level -2	10	5 mg every other day x 10
Dose Level -3	5	5 mg every other day X 10

If drug-related grade 3 or 4 non-hematologic toxicity is attributable to one or both of the drugs, dose interruption of that particular drug(s) is mandatory. Patient who experience grade 3 drug related non-hematological toxicity may be given a subsequent course one dose level below the previous course, but the patient must have recovered to grade ≤ 1 before institution of the next course. If a patient has drug-related grade 4 non-hematologic toxicity, he/she may receive a subsequent courses at one reduced dose level after resolution of toxicity to grade ≤ 1 , only if approved by the Principal Investigator based on the clinical significance of the toxicity and only if patient has had derived a benefit from the therapy. The dose of therapeutic agents can be decreased during a cycle, at the discretion of treating physician, for chronic grade 2 non-hematologic toxicity. In specific circumstances, after discussion with the Principal Investigator, one of the two medications can be discontinued for safety. Documentation of the reason(s) study drug is discontinued is required. Other dose modifications may be considered as clinically indicated with documentation and approval of the PI

During a cycle of therapy, dosing of INCB018424 and lenalidomide will be discontinued for platelet counts $\leq 35 \times 10^9/L$ OR for ANC $\leq 500/uL$. Dosing of INCB018424 may resume at 5mg QD if the platelet count increases $> 35 \times 10^9/L$ AND ANC $> 500/uL$, and can be increased to 5mg BID for the remainder of the cycle once platelet count is $> 50 \times 10^9/L$ AND ANC $> 1000/uL$. Lenalidomide will not be restarted during this cycle.

Patients who experience platelet count $\leq 35 \times 10^9/L$ or ANC $\leq 500/uL$ during a cycle of therapy, will have a dose reduction of therapy by one dose level for subsequent

cycles. A reduction of 2 dose levels may be considered if the myelosuppression was deemed severe and life threatening by the treating physician, and if it is in the patient's best interest. Reductions in dosing for therapy related anemia can be done at the discretion of the investigator.

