Patients may be escalated to the next higher dose level if ALL of the following criteria are met (for the study drug being dose escalated). (Applicable also for patients receiving only one study drug)

1. no dose reductions due to toxicity were required in the prior 2 cycles
2. no dose interruptions due to toxicity were required in the prior 2 cycles
3. the prior cycle was not delayed due to toxicity
4. the current cycle is not delayed due to toxicity
5. Platelet count $\geq 100 \times 10^9/L$ AND ANC $\geq 1000/uL$
6. The patient has sub-optimal benefit defined as a failure to reduce palpable spleen length by at least 50% and/or suboptimal improvement in MF related symptoms as assessed by the investigator, and/or failure to improve cytopenia
7. no development of new onset transfusion dependency

Dose modifications/discontinuation for prednisone therapy will be at the discretion of the clinician but must be documented clearly when it happens. Prednisone dose modification/discontinuation will not require withdrawal from the study. Treatment of hyperglycemia with either oral hypoglycemic agents or insulin does not necessarily require discontinuation of prednisone if the hyperglycemia is controlled with these medications.

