8.0 STATISTICAL CONSIDERATIONS

All subjects meeting the eligibility criteria that have signed a consent form and have begun treatment will be evaluable for response. This is a two stage, phase II trial designed to assess the effect of therapy in subjects with Primary, Post Polycythemia Vera, or Post Essential Thrombocythemia Myelofibrosis (PMF, post-PV MF, or post-ET MF). Secondary objective is to determine the safety of therapy in this population.

The primary objective of this study is to assess efficacy in terms of the objective response rate (complete and partial response, and clinical improvement by IWG-MRT) in patients with MF. The Min-Max two-stage design proposed by Simon will be implemented. Sample size and decision criteria are chosen to reduce the expected accrual if the treatment is ineffective in regard to response relative to having no interim stopping rule. The target response rate is 50%. A response rate of 35% or less will be considered unacceptable and treatment with the therapy will be discontinued. Given the response rates stated above, if the probability of inappropriately accepting a poor therapy is 10% ($\alpha=0.1$), a total sample size of 49 patients will result in 80% power ($\beta=0.2$).

In the first stage of the design, a total of 31 patients will be enrolled and the study will be put on hold to assess response. If 10 or fewer patients respond to the combination therapy, after being treated for 6 months or discontinued due to excessive toxicity or lack of efficacy, then the study will be terminated and the therapy will be declared ineffective. Those patients who stopped receiving one of the two study drugs due to safety reasons will be counted as failures in the efficacy analysis. However, if 11 or more patients respond, up to an additional 18 patients will be enrolled to complete the study.

After a total of 49 patients have been enrolled into the study, if 21 or fewer patients respond to the therapy, the therapy will be declared ineffective. However, if greater than 21 patients respond to the therapy, the therapy will be considered efficacious. The probability of early termination due to unacceptable response rate is 46% under the null hypothesis.

Data from all subjects who receive any study drug will be included in the safety analyses. Subjects who entered the study and did not take any of the study drug and had this confirmed, will not be evaluated for safety.

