This phase II clinical trial will have a stopping rule based on toxicity defined as an adverse events considered to be at least possibly related to treatment. In particular, accrual to the study will be temporarily suspended if: a) 2 or more among the first 10 subjects treated on this trial experiences a Grade 4 non-hematologic toxicity or a

serious adverse event that is felt to be drug related. b) 20% or more of subjects (when more than 10 subjects have been accrued) experience a Grade 4 non-hematologic toxicity or serious adverse event that is felt to be drug related. After consideration by the study team (study chair, statistician), a decision will be made as to whether accrual can resumed after approval of the appropriate IRB.

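### Harm confined to patients escalated above level 0 can stay below the 20% toxicity boundary, because the rule counts all subjects together and no safety summary by dose is planned

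*Combined protocol and SAP*

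**What the plan says.** - **Starting dose, Section 5.0.** "The planned dose and schedule of investigation of INCB018424 is 15 mg orally twice daily (BID), continuously in 28-day cycles", with lenalidomide 5 mg/day on days 1-21. This matches level 0 (15 / 5) in the Section 5.1 table and confirms how its columns read.
- **Top level, Section 5.1.** The table gives "Dose Level +3 25 15": INCB018424 25 mg BID with lenalidomide 15 mg.
- **Escalation, Section 5.1.** "Patients may be escalated to the next higher dose level if ALL of the following criteria are met". Seven criteria follow, covering recent toxicity, blood counts, insufficient benefit and new transfusion dependency.
- **Cited experience, Sections 2.2 and 2.3.** For INCB018424 alone: "The initial dose-escalation phase established 25 mg twice daily or 100 mg once daily as maximum tolerated doses, on the basis of reversible thrombocytopenia". For single-agent lenalidomide: "Protocol treatment consisted of oral lenalidomide at 10 mg/d". With prednisone: "Therapy consisted of lenalidomide 10 mg/d". Both lenalidomide reports used 5 mg/d when platelets were low.
- **Safety set, Section 8.0.** "Data from all subjects who receive any study drug will be included in the safety analyses". Section 8.0 mentions no tabulation by dose.
- **Toxicity rule, Section 8.0.** Accrual is suspended temporarily if 2 or more of the first 10 subjects have a qualifying event, and later if "20% or more of subjects (when more than 10 subjects have been accrued) experience a Grade 4 non-hematologic toxicity or serious adverse event" judged drug related. Neither limb refers to dose level. The study team then reviews, and accrual resumes only with IRB approval.

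**The concern.** Safety of the combination is the secondary objective, and level +3 is the level furthest from the cited experience. Only patients who have tolerated lower levels, and whose benefit is insufficient, can get there, so they are likely to be a minority. When their events are divided by all treated subjects, a high rate at that level becomes a modest overall rate.

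Two features of the rule add to this:

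- It counts hematologic toxicity only when it is a drug-related serious adverse event, although the cited maximum tolerated dose was set on thrombocytopenia.
- Its only action is on accrual. On a literal reading of the two-cycle look-back, +1 is possible from cycle 3, +2 from cycle 4 and +3 from cycle 5. Events at +3 may therefore come after much of accrual is complete.

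At stake is whether the trial can see, and later report, that one level is more toxic than the rest.

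**Working it through.** **Inputs from the documents.** Stage sizes are 31 and 49, and the boundaries are 2 of the first 10, then 20% (Section 8.0). Doses come from Sections 2.2, 2.3, 5.0 and 5.1. The plan gives no operating characteristics for the toxicity rule, so there is no figure of that kind to reproduce. The two-stage response design behind the sample sizes does reproduce: with 10/31 and 21/49 at 35% and 50%, early termination under the null is 0.455 (plan: 46%), alpha is 0.097 and power is 0.801.

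**Step 1, doses.** For INCB018424, +3 is 25/25 = 1.0 times the cited single-agent maximum. For lenalidomide it is 15/10 = 1.5 times the highest cited myelofibrosis dose. Levels +1 (20 / 5) and +2 (20 / 10) exceed neither.

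**Step 2, boundary.** 0.20 × 31 = 6.2, so 7 events are needed. 0.20 × 49 = 9.8, so 10 are needed. With no other events, 6 of 6 escalated patients (6/31 = 19.4%) or 9 of 9 (9/49 = 18.4%) do not cross the 20% limb. This needs no assumed rate.

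**Step 3, chance of crossing.** The number reaching +3 and all event rates are assumptions. Let 8 of 49 reach +3 with a 60% event rate there, and let the other 41 have background rate b. The total is Bin(8, 0.6) + Bin(41, b), and the expected pooled rate is (4.8 + 41b)/49. The single-look column is exact. The last two columns are simulated, with +3 patients placed at random in enrolment order and events counted at enrolment.

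| b | Pooled rate | 10 or more of 49, single look | Adding the first-10 limb | Checked after every patient |
|---|---|---|---|---|
| 3% | 12.3% | 3% | 36% | 46% |
| 5% | 14.0% | 9% | 45% | 57% |
| 10% | 18.2% | 39% | 67-68% | 78-79% |
| 15% | 22.3% | 70% | 85% | 91% |

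Counting events at enrolment favours the rule, since +3 is not reached before cycle 5. With 6 patients at +3 and a 40% rate there, the single-look chance is 0.1% at b = 3% and 11% at b = 10%. Checking after every patient at b = 3% gives about 20%.

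A crossing at a high background also says little about +3. If every patient has a 10% rate, the rule checked after every patient triggers in about 33% of trials.

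**Step 4, one count for escalated patients.** Assume 20 patients go above level 0, 8 of them reach +3 at 60%, and the other 12 have a 3% rate. The 20% threshold is 4 of 20, and P(Bin(8, 0.6) + Bin(12, 0.03) ≥ 4) = 87%. With 15 escalated patients the threshold is 3, and the chance is 96%.

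**Step 5, false alarms.** At a true 10% rate, P(2 or more of 10) = 1 − 0.9^10 − 10 × 0.1 × 0.9^9 = 1 − 0.349 − 0.387 = 26%. Continued checking up to 15 to 25 escalated patients raises this to about 30% to 32% (simulation).

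A separate boundary at each of the three higher levels, with independent 10% rates, gives at least one false crossing in about 60% of trials for 20, 14 and 8 patients, and about 54% for 15, 10 and 6.

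**The case against.** The strongest reply is that patients are already protected. Escalation requires platelets of at least 100 × 10⁹/L, adequate neutrophils, two cycles without toxicity-driven reduction or interruption, and no toxicity delay. Section 5.1 interrupts the responsible drug for related Grade 3-4 non-hematologic toxicity, and it stops dosing and lowers the level for low counts. Section 7 sends every serious event to the IND Office and attributed events to the manufacturers. A run of 9 in 9 would hardly go unnoticed. This stands as far as individual risk goes. It does not show whether a level is too toxic for the next patient, and it does not produce a safety estimate by dose.

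Three stronger readings are tempting, and the documents do not support them:

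- **That +3 contradicts the maximum tolerated dose.** It equals the cited figure and does not exceed it. Section 2.2 also reports titration from 15 mg BID as the preferred single-agent regimen. What is missing is a statement about the combination.
- **That the plan commits to pooled reporting only.** The Section 8.0 sentence defines who is in the safety set. No summary by dose is planned, but none is excluded.
- **That the rule would almost always miss such harm.** The 3% figure belongs to one assumed background rate and a single look. Section 8.0 does not fix the number of looks.

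It is also fair to object that a within-group count using the same events still misses thrombocytopenia that is not serious. For that reason the table in the fix includes hematologic events.

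**Conclusion.** The concern holds as a gap in monitoring and reporting. On the documents alone, the toxicity rule has no dose stratum, no safety summary by dose is planned, and 9 affected patients among 49 do not cross the boundary even if all 9 are at the top level. How likely a miss is cannot be settled from the documents. In the 8-patient, 60% example the rule triggers with probability between 3% and 91%, depending on the background rate and on how often the rule is checked. Dilution is worst when few patients reach +3 and other events are rare. Even when the rule triggers, it does not show at which dose the events arose.

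A reader might infer that each level needs its own stopping boundary. The false-crossing rate of about 54% to 60% argues against that. The table by dose is a clear and cheap improvement; a single count for escalated patients is a reasonable addition.

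**What to change.** 1. **Table by dose (Section 8.0).** Tabulate drug-related adverse events, including Grade 3-4 hematologic events, by the dose of each drug in force at onset. Use patients and cycles at that dose as denominators. Use each drug's own dose, because the Section 5.1 criteria apply to the drug being escalated and to patients on one drug, so patients need not sit on a paired level. Note beside the table that escalated patients are a selected group.
2. **One count for escalated patients (Section 8.0).** Count qualifying events among all patients who have had either drug above its level 0 dose, against the existing threshold (2 of the first 10, then 20%). Make a crossing a trigger for the study-team and IRB review already described, not an automatic suspension. State how often it is checked and its false-alarm rate: 26% at 2 or more of 10 with a true 10% rate, somewhat higher with continued checking.
3. **Relation to cited doses (Section 5.1).** State how level +3 relates to the figures in Sections 2.2 and 2.3. Which doses are right is for the clinical team.

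The cost is protocol wording, one more table from the diaries and drug counts that Section 5.0 already requires, and some extra reviews. Sample size and response boundaries do not change.
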